4.6 Other Analyses

Not applicable.

4.6.1 Other Variables and/or Parameters

Not applicable.

4.6.2 Subgroup Analysis

The following subgroups will be defined (ATC codes to identify the respective previous systemic treatments are given in brackets):

- EASI score at baseline (\leq /> median),
- vIGA-AD at baseline (=3 / =4),
- BSA affected by AD at baseline (\leq /> median),
- Weekly average of the Peak Pruritus 0-10 numerical rating scale (NRS) score at baseline (≤ / > median),
- IgE level at baseline (<300 kU/L, 300-1000 kU/L, > 1000 kU/L),
- age $\geq 18 <40, \geq 40 <= 65,$
- age of onset of AD (<18 / >=18 years),
- sex,
- race,
- body mass index (BMI) at baseline (<25, 25 30, >30),
- previous treatment with systemic standard of care for AD within 6 months (i.e. 183 days) before start of study drug (yes/no) (refer to Section 6.3 for a list with respective medication).
- previous treatment with systemic glucocorticoids/ non-steroidal systemic immunosuppressants/ calcineurin inhibitors for AD (Yes/No)
 (1024 D/102DX Classical definition of the state of the
 - (- H02AB/H02BX Glucocorticoids for systemic use
 - L04AA06 MMF (Mycophenolic acid, Mycophenolate sodium, Mycophenolate acid, Mycophenolate mofetil)
 - L04AX01 Purine antagonist Azathioprine
 - L04AX03, L01BA01 Antineoplastic folic acid analogues Methotrexate
 - L04AD 01 Ciclosporin
 - L04AD 02 Tacrolimus
 - L04AD 03 Voclosporin),
- previous treatment with Dupilumab/Tralokinumab for AD (Yes/No) (- D11AH05, IL-4 and IL-13 monoclonal antibody – Dupilumab
 - D11AH07 IL-13 antibodies – Tralokinumab),
- previous treatment with JAK inhibitor for AD (Yes/No)
 (-L04AA37 JAK-inhibitor Baricitinib
 - L04AA44 JAK-inhibitor Upadacitinib
 - D11AH08 JAK-inhibitor Abrocitinib).

Previous treatment for AD refers to treatment used within 6 months (i. e. 183 days) before treatment start with indication "treatment of atopic dermatitis related symptoms".

The median for subgroup definitions will be calculated based on the respective analysis set used for subgroup analysis.

Frequencies of EASI 75 response (imputation according to B1_1 in Table 4-1) and summary statistics of percent change in EASI from baseline at Day 84 (Visit 7) (imputation according to C1_1 in Table 4-2) broken down by subgroups will be provided.

4.7 Interim Analyses

An interim analysis will be performed using the data of all study participants having either regularly completed or prematurely discontinued study intervention at a certain cutoff date, when a minimum of 80% of patients are evaluable. The eligibility of the respective study participants for the analysis sets will be checked and documented before unblinding for the interim analysis. Study intervention of participants not having completed the intervention period by the time of the interim analysis will not be unblinded. Access to the treatment codes of the participants included in the interim analysis prior to final database release will be restricted to an unblinded team, whereas the rest of the team remains blinded. No individual data of the interim analysis will be disclosed to the blinded study team responsible for further study conduct. Details of the measures to restrict access to unblinding data will be described in detail in a dedicated study blinding plan. The further study conduct or study design will not be affected by the results of the interim analysis.

An administrative interim analysis will be performed using the data of all study participants randomized until a certain date (02-AUG-2023). Approximately 90% of all participants have been randomized until this date and will be part of the interim analysis. The data cut-off for the interim analysis will be performed after all these participants have either regularly completed or prematurely discontinued study intervention and have primary efficacy data. The eligibility of the respective study participants for the analysis sets relevant for the interim analysis (SAS, FAS, PPS) will be checked and documented before unblinding for the interim analysis. Details of the measures to restrict access to unblinding data will be described in detail in a dedicated study blinding plan which will be signed before unblinding of the interim data.

A subset of the outputs planned for the final analysis will be provided for the interim analysis. The focus of the interim analysis will be the primary and secondary efficacy endpoints as well as the frequency of adverse events. The outputs will be provided in such a way that no unblinding on individual subject level will be possible. For summary statistics, only the number of subjects, the mean and standard deviation will be provided given that the number of participants per treatment group is at least 3. For frequency tables, number and percent of participants by treatment group will generally only be presented if there is at least one participant per treatment group with the event being counted or none in both treatment groups. In case of frequencies for related categories (e. g. several age categories) special care will be taken that there is no unblinding via total number of subjects per treatment group. For example, if there is one category with only one subject where frequencies by treatment group will not be presented the treatment of the subject could be derived by the numbers in the other categories by treatment group and total number of subjects by treatment group. In such a case the category with the next smallest total frequency will also only be presented with total frequency, not frequencies by treatment group. Total frequencies for both treatment groups combined can always be presented. Frequencies for the binary efficacy endpoints will be presented by treatment group to allow assessment of the efficacy of zabedosertib. However,

the individual post-dose data of these efficacy endpoints are stored in such a way that Bayer colleagues who will see the interim results either don't have access to this data or will not participate in further study conduct and blind data review meeting until unblinding for the final analysis.

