8.3 Assessment of intercurrent events

Identification of intercurrent event "use of rescue medication"

All medication on the concomitant medication page that is rescue medication according to the protocol and used at or after treatment start will be identified:

- topical corticosteroids (TCS) (Defined rescue medication for this study is the methylprednisolone aceponate (Advantan® cream). Only if Advantan cream is not available in the respective country, an alternative TCS with similar potency may be used (see WHO definition for potent corticosteroids group III, such as betamethasone, fluclorolone, desoximetasone, fluocinolone acetonide, budesonide, mometasone, beclomethasone, hydrocortisone aceponate))
- topical calcineurin inhibitors (TCI) (If TCSs are not tolerated or their use is not advisable, the topical TCIs pimecrolimus 1% (Elidel® cream) or tacrolimus (Protopic® 0.1% or 0.03% ointment) may be used.

Rescue medication will be identified by the following ATC codes if route of administration is topical or cutaneous (in case of multiple possible potency groups for corticosteroids the highest possible potency will be considered):

- Corticosteroids, potent (group III) (D07AC, D07BC, D07CC, D07XC),
- Corticosteroids, very potent (group IV) (D07AD, D07BD, D07CD, D07XD),
- Agents for dermatitis, excluding corticosteroids:
 - Calcineurin-inhibitors Tacrolimus (D11AH01),
 - Calcineurin-inhibitors Pimecrolimus (D11AH02)

The occurrence of the intercurrent event "use of rescue medication" will be applicable if the indication for use of an above listed topical medication is

• "rescue treatment: protocol specified"

or if the indication is

• "treatment of atopic dermatitis related symptoms"

or if the indication is

- "adverse event" and the adverse event is consistent with the indication AD Adverse events will be classified as consistent with AD or not during blind data review by persons without access to any individual post-dose efficacy data. The following AEs will always be considered to be consistant with AD:
 - PT: Dermatitis atopic,
 - PT: Neurodermatitis,
 - PT: Eczema.

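### The interim display rule blanks the by-arm split only when one arm has no events, so a blank adverse event row with two or more participants shows that they share an arm

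*SAP*

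**What the plan says.** SAP 4.7 plans an administrative interim analysis on roughly 90% of participants. It focuses on the primary and secondary efficacy endpoints "as well as the frequency of adverse events". Part of the team stays blinded, and the section states its aim plainly: "The outputs will be provided in such a way that no unblinding on individual subject level will be possible".

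For frequency tables it gives these rules:

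- Numbers and percentages "by treatment group will generally only be presented if there is at least one participant per treatment group with the event being counted". The one other case in which the split appears is a row without any events, which the rule words as "or none in both treatment groups".
- "Total frequencies for both treatment groups combined can always be presented".
- In tables of related categories, where a suppressed cell could be recovered by subtraction, a second row is blanked too: "In such a case the category with the next smallest total frequency will also only be presented with total frequency".
- Binary efficacy endpoints are exempt: "Frequencies for the binary efficacy endpoints will be presented by treatment group". The safeguard attached to this exemption is that sponsor staff who see interim results either cannot reach the individual post-dose data for those efficacy endpoints or take no part in later conduct and blind review.

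The minimum of three participants per arm applies to summary statistics, not to frequency tables. Further access controls are left to a separate blinding plan.

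Individual AE data are needed later. SAP 8.3 states: "Adverse events will be classified as consistent with AD or not during blind data review". That task is given to people without access to individual post-dose efficacy data.

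**The concern.** A suppression rule protects the blind only if the decision to suppress carries no information about what is suppressed. Here the decision depends on the split itself. The SAP's worked example deals with recovering one participant's arm by subtraction across categories. It does not deal with the blank cell being informative.

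The people who can use the information are those who see interim outputs and also hold individual AE data, because they know which participants make up a row. The separation in 4.7 does not exclude them. Someone without individual efficacy data may see the interim results and still join the blind review, and that describes the people whom 8.3 assigns to classify AEs.

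Two things are at stake: the integrity of the blind for anyone still making judgements on AEs, and the usefulness of an interim AE display that cannot show by arm an event seen in one arm only.

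**Working it through.** **Step 1: what a blank means.** Let a and b be the numbers with the event on zabedosertib and placebo. The split is shown if (a ≥ 1 and b ≥ 1) or (a = 0 and b = 0). The complement is that exactly one of a and b is zero. Enumerating every pair with a from 0 to 48 and b from 0 to 24 gives no exception. A stand-alone row with total k > 0 and a blank split is therefore k:0 or 0:k.

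**Step 2: how far the blank points to one arm.** The plan gives no figure to reproduce, so the inputs are partly assumed:

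- 72 randomized at 2:1 (SAP 5), about 90% in the interim (SAP 4.7): 0.9 × 72 ≈ 65.
- Assumed interim split 43:22, and no drug effect on the event.

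Formulas:

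- P(blank | k) = [C(43,k) + C(22,k)] / C(65,k)
- P(zabedosertib | blank, k) = C(43,k) / [C(43,k) + C(22,k)]

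| k | P(blank) | P(zabedosertib given blank) |
|---|---|---|
| 1 | 65/65 = 100% | 43/65 = 66% |
| 2 | (903 + 231)/2,080 = 55% | 903/1,134 = 80% |
| 3 | (12,341 + 1,540)/43,680 = 32% | 12,341/13,881 = 89% |
| 4 | (123,410 + 7,315)/677,040 = 19% | 123,410/130,725 = 94% |

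For k = 1 the blank adds nothing to the allocation ratio. Disclosure starts at k = 2. With all 72 participants (48:24) the last column is 67%, 80%, 89% and 95%, so the result hardly depends on the assumed interim size.

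**Step 3: one-sided events.** Any split x:0 is blanked, however large x is: 1 versus 1 is shown and 8 versus 0 is not. For true rates p_z on zabedosertib and p_p on placebo, the chance that a row is blanked as zabedosertib-only is (1 − p_p)^22 × [1 − (1 − p_z)^43]. The rates below are illustrative assumptions:

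- 10% versus 2%: 0.641 × 0.989 = 63%
- 10% versus 1%: 0.802 × 0.989 = 79%
- 10% versus 0%: 1 × 0.989 = 99%

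The pooled total remains visible in each case.

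**The case against.** The best case on the other side has four parts.

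- **A blank does not name an arm.** At k = 2 it moves the probability from 66% to 80%, whereas printing the split would give certainty. In related-category tables a row may also be blank through companion suppression. Both points stand: the leak is partial, and the inference is exact only for stand-alone rows such as a single AE term. But if one member's treatment becomes known, so does that of the whole row.

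- **The order of events protects the primary endpoint.** Eligibility of interim participants for the analysis sets is checked and documented before interim unblinding. Per-protocol and full-analysis-set membership uses the rescue, standard-of-care and lack-of-efficacy events of SAP 8.3, so most of the relevant AE classifications should, by inference, already be made. Participants outside the interim are not in its tables. Discretion is also narrower than it may look: recorded indications count directly, and listed preferred terms are always taken as consistent with atopic dermatitis. This largely stands. What remains is that SAP 3 leaves final set assignment to the later blind review, so classifications can be reopened and AEs can arise in between.

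- **The distribution of outputs is not known.** The blinding plan and table specifications are separate documents, only a subset of outputs is planned, and the rule says that it applies generally. This is a fair limit. Even so, 4.7 itself sets the rule and claims that it prevents individual unblinding, and the separation it describes does not reach AE data.

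- **The interim is administrative.** It changes neither conduct nor design, and the rule is not stated for the final safety tables. This stands, and it limits the weight of the one-sided AE point.

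**Conclusion.** The rule does not secure the aim set out in SAP 4.7 for readers who hold individual AE data. In a stand-alone AE row with k ≥ 2, a blank split shows that all k participants share an arm, and 2:1 allocation makes zabedosertib the likely one: 80%, 89% and 94% for k = 2, 3 and 4, against 66% from allocation alone. These figures assume a 43:22 interim split and no drug effect. That blinded staff with AE data receive such rows is possible under 4.7 but not established.

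Three stronger readings are tempting and not supported:

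- A reader might infer that a blank row reveals a participant's treatment. It shifts a probability; it does not identify the arm.
- A reader might infer that partly unblinded staff would be setting the primary endpoint. The documented eligibility check before interim unblinding leaves only reopened classifications and AEs arising before the final blind review.
- A reader might infer that zabedosertib-only AEs are concealed. Only the interim split is withheld; pooled totals can be shown, and the restricted team holds the treatment codes. Nothing in the documents makes this interim a safety review that must display one-sided events.

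This is a cheap improvement to the blinding safeguards, not a threat to the final analysis.

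**What to change.** For interim AE frequency tables, adopt a rule that does not depend on the split:

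- Anyone who holds individual AE data and takes part in further conduct or blind review sees pooled totals only, for every AE row.
- Complete by-arm AE tables, without suppression, go only to the restricted unblinded team already defined in SAP 4.7.

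An equivalent route is to extend the existing separation for individual efficacy data to individual AE data, so that nobody who sees by-arm interim AE output can both hold those data and take part in further conduct or blind review.

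Keep the present rule, including companion suppression, for other frequency tables; this change supplies no replacement for them.

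The cost is wording in SAP 4.7 and the blinding plan and one extra version of the AE tables. The downside is that blinded staff see no by-arm AE counts before final unblinding. Data collection, sample size and the final analysis are unchanged.

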	Participants will be analyzed according to the treatment they actually received.
Biomarker analysis	All participants who
set (BAS)	 showed compliance of at least 80% with study intervention during the last 4 weeks before end of treatment
	 have at least 1 valid biomarker sample at baseline and post-dose (blood sample or biopsy),
	 are without validity findings, which would interfere with the evaluation of the biomarker data,
	- are without validity findings with respect to the main efficacy related entry criteria
	Participants will be analyzed according to the treatment they actually received.

Final decisions regarding the assignment of participants to analysis sets will be made during the blind review of study data and documented in the final list of important deviations, validity findings and assignment to analysis set(s). Any case-by-case decision concerning

validity will be taken during the blind review by persons without access to any individual post-dose efficacy data to avoid any potential bias.

Please also refer to Section 8.3 for the assessment of the intercurrent events "use of rescue medication", "use of systemic standard of care (SoC)", and "discontinuation of study intervention due to lack of efficacy" and Section 4.5.1 for the calculation of compliance used in the definition of the analysis sets FAS and PPS.

4. Statistical Analyses

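### Staff who have seen by-arm interim results may join the later blind review, and the SAP does not say that analysis-set and intercurrent-event decisions made before interim unblinding are final.

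*SAP*

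**What the plan says.** **The interim (SAP 4.7).** It covers everyone randomized up to 2 August 2023: "Approximately 90% of all participants have been randomized until this date". On what is shown, the SAP says: "Frequencies for the binary efficacy endpoints will be presented by treatment group to allow assessment of the efficacy of zabedosertib". These endpoints include the primary one.

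**Who may do what afterwards (SAP 4.7).** Staff who see the results must "either don't have access to this data or will not participate in further study conduct and blind data review meeting until unblinding". The data meant are the individual post-dose values of the efficacy endpoints. Treatment codes go only to an unblinded team. For the others the SAP says: "No individual data of the interim analysis will be disclosed to the blinded study team responsible for further study conduct". That sentence covers individual data and does not name aggregate by-arm results.

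**What the blind review decides.**
- SAP 3 places the final assignment to analysis sets in that review. The sentence beginning "Any case-by-case decision concerning" validity sets one condition on the people deciding: no access to individual post-dose efficacy data.
- SAP 8.3 applies the same condition to the medication-related intercurrent events: "Adverse events will be classified as consistent with AD or not during blind data review". It does likewise for adverse events that led to stopping treatment and may reflect lack of efficacy.
- SAP 4.5.1 sends unresolved conflicts between diary and tablet count to the same review. These bear on the 80% compliance criteria of the PPS.

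**Safeguards already present.** Eligibility of interim participants for the analysis sets is checked and documented before interim unblinding. A blinding plan is to be signed first. On the outputs, SAP 4.7 says: "The outputs will be provided in such a way that no unblinding on individual subject level will be possible".

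**The concern.** The two conditions in SAP 4.7 are joined by an or. The attendance bar therefore applies only to people who hold individual post-dose efficacy data. Knowing the by-arm response frequencies does not keep anyone out, and neither SAP 3 nor SAP 8.3 adds that condition.

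The review's decisions feed the primary analysis, which is run on the PPS. Under the primary estimand (SAP 1.1), a discontinuation labelled lack of efficacy is a non-response. The same discontinuation labelled otherwise is imputed if it occurs at or after Day 56, and leads to exclusion if it occurs earlier. A judgement on diary reliability can move a participant into or out of the PPS. If a reviewer knows which way the result leans and how far it is from the 90% criterion, a residual rule, such as whether an unlisted term counts as lack of efficacy, is no longer set in ignorance of the result.

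**Working it through.** **1. Does any section close the gap?** Take a sponsor employee who has seen the by-arm interim frequencies but has no individual post-dose efficacy data.

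| Place | Test applied | Is this person barred? |
|---|---|---|
| SAP 4.7, attendance | No individual efficacy data, or stay out | No |
| SAP 4.7, blinded team | No individual interim data or treatment codes | No; aggregates are not named |
| SAP 3, validity decisions | No individual post-dose efficacy data | No |
| SAP 8.3, adverse-event classification | No individual post-dose efficacy data | No |
| SAP 4.5.1, diary reliability | None stated beyond blind review | No |

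**2. Are the pre-interim decisions final?** SAP 4.7 says that analysis-set eligibility is checked and documented. SAP 3 says that final decisions are taken at the blind review. Nothing in SAP 4.7 makes the documented status binding, and it does not mention intercurrent-event classifications.

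**3. How many participants are outside the interim?** With 72 planned and about 90% included, 0.90 × 72 = 64.8 are inside and 0.10 × 72 = 7.2, about 7, are outside.

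**4. How sensitive is the criterion to one decision?** Inputs from SAP 4.2.2 and 5: Beta(1,1) priors, 38 and 19 evaluable participants, success if the posterior probability exceeds 0.90, assumed response rates 0.49 and 0.16. With k responders among n in each arm (B for zabedosertib, P for placebo),

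P(π_B > π_P | data) = ∫ f(x; k_B+1, n_B−k_B+1) · F(x; k_P+1, n_P−k_P+1) dx,

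where f and F are the Beta density and distribution function.

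*The plan's own figure first.* Summing the binomial probabilities of all outcomes that meet the criterion gives a power of 0.910, so the stated figure of at least 90% reproduces.

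*Illustration with assumed counts, not trial data.* Start from 12/38 versus 3/19, posterior 0.885, criterion not met. Rows change one participant, except the last.

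| Change | Counts | Posterior | Shift |
|---|---|---|---|
| Exclude one zabedosertib non-responder | 12/37 vs 3/19 | 0.896 | +0.011 |
| Exclude one placebo non-responder | 12/38 vs 3/18 | 0.863 | −0.022 |
| Exclude one zabedosertib responder | 11/37 vs 3/19 | 0.855 | −0.030 |
| Zabedosertib non-responder becomes responder | 13/38 vs 3/19 | 0.918 | +0.033 |
| Zabedosertib responder becomes non-responder | 11/38 vs 3/19 | 0.841 | −0.043 |
| Exclude one placebo responder | 12/38 vs 2/18 | 0.943 | +0.058 |
| Placebo responder becomes non-responder | 12/38 vs 2/19 | 0.953 | +0.069 |
| Placebo non-responder becomes responder | 12/38 vs 4/19 | 0.776 | −0.108 |
| Exclude two zabedosertib non-responders | 12/36 vs 3/19 | 0.906 | +0.022 |

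Single changes from this start move the posterior by 0.011 to 0.108 in absolute size. In a close result, one or two decisions can cross 0.90. This measures sensitivity to any single decision. It does not measure bias from the attendance rule.

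**The case against.** The strongest reply is that little is left to influence.

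- **No direct lever.** The reviewer in question knows neither a participant's treatment nor that participant's efficacy data, so a decision cannot be directed towards an arm. This stands, and it makes the risk indirect.
- **Suppressed outputs.** By-arm frequencies are generally shown only if both arms have the event or neither has. Related categories are masked where a treatment could be derived by subtraction. This stands for adverse events. The binary efficacy endpoints are the stated exception.
- **Pre-fixed terms.** SAP 8.3 lists terms always counted as consistent with AD and terms always counted as lack of efficacy. Only unlisted terms are judged at the meeting. This stands.
- **Decisions already taken.** PPS membership depends on rescue use, SoC use, lack-of-efficacy discontinuation and compliance. The interim cannot report the primary endpoint without classifying these. Most calls for about 90% of participants should therefore exist before anyone sees results. That is a fair inference, but the SAP does not state it and does not freeze the calls.
- **Other analyses.** Sensitivity analysis B_1.2 and FAS analysis B_6.1 score both kinds of discontinuation as non-response, and the FAS has no compliance criterion. This limits the reach of a reclassification there, apart from its effect on set membership. It does not protect the primary analysis.
- **The blinding plan.** It may be stricter. It is not among the documents, and the SAP states a permissive attendance rule of its own.
- **Context.** The study is exploratory and the interim is not to affect conduct or design. This bears on severity. The point here concerns decisions for the final analysis.

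A reader might infer that people who know the results can steer individual participants by arm, or that PPS membership of the whole interim population is decided afresh after unblinding. The documents support neither: codes and individual efficacy data are withheld, and eligibility is documented beforehand.

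**Conclusion.** The gap in the text is clear: seeing by-arm interim efficacy results is not a bar to the blind review, and decisions documented before interim unblinding are not declared final. The exposure is small and indirect. It concerns about 7 of 72 participants, any reopened case, and classification of adverse events not listed in advance.

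The size of any bias cannot be estimated from the documents. The 0.01 to 0.11 range rests on assumed counts just below the criterion and on the planned 38 and 19 evaluable participants. It shows only that a close result could turn on one or two decisions. Other starting counts give other ranges. The conclusion also assumes that the unseen blinding plan does not already exclude these people. This is an inexpensive improvement and does not undermine the design.

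**What to change.** Add two statements to SAP 3 and 4.7 and carry them into the blinding plan:

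1. For participants in the interim, analysis-set assignments and intercurrent-event classifications are documented before interim unblinding and are final, except for data corrections, each logged with its reason.
2. For the remaining participants (about 10%), and for any reopened case, these decisions are made only by people who have not seen by-arm interim results, whatever their access to individual efficacy data.

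The first statement removes most of the risk and needs no extra staff. The second covers what is left. Sample size, power and the analysis model do not change. The cost is two sentences and slightly less freedom over who attends the review.
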